Statistical analysis plan (SAP)

Section 1. Administrative information

1a. Title, registration, versions and revisions

Full study title: Effectiveness of Written Dietary Advice on Lipoproteins - a Pragmatic Randomized Controlled Trial

Acronym: MYDICLIN

1b. Clinicaltrials.gov identifier: NCT03528252

2. SAP version: 1.4, 2019-04-18

3. Protocol version: Research plan version 18-09-20

4. SAP revisions: No major revisions.

5. Roles and responsibility

Author: [name]^{1,2}

Principle Investigator: [name]^{1,2}

Affiliations:

- 1. Unit for Clinical Nutrition and Metabolism, Deptartment of Public Health and Caring Sciences, Uppsala university.
- 2. Center for Clinical research Dalarna

6. Signatures:

I the undersigned, certify that I have read this SAP and approve it as adequate in scope of the main analyses of MYDICLIN.

6. Author and principle investigator

Name: [name]

Date: 2019 - 04 - 18

Section 2. Introduction

7. Background and rationale

Dietary factors are of major importance for public health, but effective means are lacking, to improve dietary habits of patients in primary care. This pragmatic trial aims to investigate whether detailed written dietary advice may be an effective way of improving blood lipoproteins in a Swedish primary care setting.

8. Objectives

The main purpose is to investigate whether written dietary advice with individual written feedback can affect blood lipoproteins in the short-term (3 weeks) and medium-term (6 months).

Specific aims

- What effect does written dietary advice have on LDL cholesterol (primary outcome) and other lipoproteins and risk factors (secondary outcomes) after 3 weeks and 6 months, compared with a control group?
- What proportion of individuals achieve a ≥10% reduction in LDL cholesterol from baseline, after and 6 months?
- In the group of responders (≥10% reduction in LDL cholesterol from baseline), what is the effect after 3 weeks and 6 months?
- Is double sampling of LDL cholesterol required in clinical practice, i.e., how many would be misclassified as responders/non-responders if only one sample was taken at 3 weeks and 6 months?
- How does the intervention's cost compare with estimated future health care savings, as estimated per mean LDL cholesterol reduction, and per individual reaching ≥10% reduction in LDL cholesterol at 6 months?
- Which food choices are associated with reductions in LDL cholesterol in practice?

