P<0.05 will be considered as statistically significant for primary outcomes. For secondary outcomes, significance testing is not as essential as they are mainly hypothesis generating.

17. Adjustment for multiple analyses

The primary outcome is change in LDL cholesterol at 3 weeks and 6 months. The power calculations have been performed for between-group differences at 6 months and this analysis is considered the primary outcome of the study. Thus, no adjustment for multiple analyses will be performed.

18. Confidence intervals

N/A.

Adherence and protocol deviations

19a. Definition of adherence to the intervention

Being randomized and completing the trial (day 183) is considered as sufficient for adherence. For the visit at 3 weeks, no more than 2 days' deviation from protocol will be allowed. For the visit at 183 days, no more than 2 weeks' deviation will be allowed.

19b. Description how adherence will be presented

No specific information on adherence will be presented, besides no. of participants randomized and completing the trial at 3 weeks and 6 months, and no. excluded before and after randomization, with reasons.

19c. Definition of protocol deviations

Deviations from time schedule. Failing to be overnight fasting at time points 2, 4 or 6.

19d. Description of which deviations will be summarized

In cases in which blood samples are taken on the wrong day, the no. of deviations and number of days' deviation from protocol will be reported for each time point. Also, the number indivduals who failed to be completely fasting at time points 2, 4 and 6 will be given.

20. Analysis populations

Study populations will be analyzed according to intention-to-treat principles.

Section 5. Trial Population

21. Screening data

N/A (not collected).

22. Eligibility criteria

Inclusion criteria: patients listed at the health care centre, wish to improve blood lipoproteins, ages 18-99 years.

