Secondary outcomes: Change in HDL cholesterol, total cholesterol, fasting triglycerides, apo B, apo AI, apo B:AI, fasting glucose, HbA1c, systolic and diastolic blood pressure, weight, BMI and waist circumference at 6 months and 3 weeks. No. and proportion of individuals that achieve a $\leq 0\%$, > 0 to < 10% or $\geq 10\%$ reduction in LDL cholesterol from baseline, after 6 months and 3 weeks. Change in LDL cholesterol at 6 months and 3 weeks, in responders at 3 weeks (≥10% reduction in LDL cholesterol from baseline). No. and proportion of individuals misclassified at 6 months and 3 weeks with only sample 2, 4 and 6 included in analyses. Estimated cost of intervention. Associations of food choices (total no. and no. and proportion of total X:s for each dietary advice in food record table) with change in LDL cholesterol, and with HDL cholesterol, total cholesterol, fasting triglycerides, apo B, apo AI, apo B:AI, fasting glucose, HbA1c, systolic and diastolic blood pressure, weight, BMI and waist circumference at 6 months and 3 weeks. Reasons stated for wanting to improve blood lipoproteins, and associations with total no. and percentage of total of X:s in food record table and with changes in LDL cholesterol, HDL cholesterol, total cholesterol, fasting triglycerides, apo B, apo AI, apo B:AI, fasting glucose, HbA1c, systolic and diastolic blood pressure, weight, BMI and waist circumference at 6 months and 3 weeks. No. of individuals that develop impaired fasting

glucose, and elevated ALT at 6 months and 3 weeks. Change and average variation (CV) in LDL Cholesterol at 21 vs. 18 days and at 183 vs. 180 days.

Possible future analyses: Change in plasma Lipoprotein(a), serum PSCK9 and genes involved in lipid metabolism at 6 months and 3 weeks.

26b. Specific measurements and units

LDL cholesterol (direct method), HDL cholesterol, total cholesterol, fasting triglycerides and glucose in mmol/L.

Apo B and apo AI in g/L.

HbA1c in mmol/mol.

ALT in µkat/L.

TSH in mU/L.

Weight (in light clothing) in kg.

Height and waist circumference in cm.

BMI as kg/m^2 .

Systolic and diastolic blood pressure in mm hg.

Age at randomization in X.X years

Type 2 diabetes is defined according to current diagnostic criteria.

Impaired fasting glucose is defined as fasting P-glucose 6.1 - 6.9 mmol/L.

26c. Specific calculations

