For LDL Cholesterol baseline (BL) values will be calculated as the arithmetic mean of values at day -3 and day 0 [(d-3+d0)/2], similarly, values at 3 weeks will be calculated as the arithmetic mean of values at days 18 and 21 [(d18+d21)/2] and values at 6 months will be calculated as the arithmetic mean of values at days 180 and 183 [(d180+d183)/2].

For all continuous variables, absolute change from baseline (Δ) will be calculated at 3 weeks and 6 months as [Δ = 3w - BL and 6m - BL]. Relative change from baseline (% Δ) will be calculated as [% Δ = (3w - BL)/BL and (6m - BL)/BL].

As a sensitivity analysis, variables in the GLM with non-normal distribution will be log transformed (otherwise, no transformations will be performed).

Analysis methods

27a. Analysis methods and presentation of results

Between-group differences for change from baseline (Δ) in continuous variables will be significance tested using a general linear model (GLM). For LDL cholesterol, the results will be presented as a figure with boxplots displaying values at BL, 3 weeks and 6 months for each group. Also, a boxplot of Δ -values at 6 months will be presented for each group. The results will be given in a table format, displayed as mean±SD change from baseline, and P-values for difference between groups.

Difference in mean change from baseline in LDL cholesterol (and triglycerides for control group) between 21 and 18 days and 183 vs. 180 days will be analyzed with t-tests.

Secondary outcome no. 4 (success rate) i.e. the no. and proportion of individuals that achieve a $\leq 0\%$, >0 to <10% or $\geq 10\%$ reduction in LDL cholesterol from baseline will be analyzed by logistic regression, adjusted for age, sex and baseline BMI. No. of individuals that develop impaired fasting glucose will be compared between groups with Fisher's exact test (unadjusted).

Secondary outcome no. 8 (effective food choices) will be analyzed and presented as linear regressions between number of X:s for food choices 1-13 (and the total number of X:s) and change in LDL cholesterol (or Triglycerides within Control group) at 3 weeks and 6 months.

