Further, subgroup analyses will be performed in young (<65 years) vs elderly (65+) individuals, in order to establish whether results are homogenous in these subgroups, for guidance of future studies.

28. Missing data

When data are missing due to loss to follow-up, baseline values will be imputed. If only one time point 3 or 5 is missing (LDL cholesterol at d18 or d180), the mean LDL

cholesterol value will instead be assumed to be the exact value at time point 4 or 6 (d21 or d183).

29. Additional analyses

For possible future analyses (see 26a. secondary outcomes), analyses will be performed with similar methods as other continuous/categorical variables.

30. Harms

Reported adverse effects (if any) will be described in text or table format, depending on the outcome. No serious adverse effects are expected and severity will not be summarized separately.

31. Statistical software

IBM SPSS Statistics 25 will be used for all analyses.

32. References

Data management plan, standard operating procedures, dietary advice, food records and study letters will be stored separately and not provided at trial registry during the study. No statistical master file has yet been created and public access will not be granted.

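### Imputed and substituted LDL values enter the single- versus double-sample misclassification outcome and bias its proportion downward

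*SAP*

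**What the plan says.** The aim (SAP item 8, also in the protocol's Specific aims) asks "how many would be misclassified as responders/non-responders if only one sample was taken at 3 weeks and 6 months". A responder is someone whose LDL cholesterol falls by at least 10% from baseline.

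SAP item 26a turns this into a secondary outcome: "No. and proportion of individuals misclassified at 6 months and 3 weeks with only sample 2, 4 and 6 included in analyses". Samples 2, 4 and 6 are days 0, 21 and 183, so the single-sample rule compares day 21 or 183 with day 0. Under the double-sample rule in item 26c, "For LDL Cholesterol baseline (BL) values will be calculated as the arithmetic mean of values at day -3 and day 0", and the follow-up values are the corresponding means of days 18/21 and 180/183.

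Three further statements decide who is counted and with what values:

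- Item 20: "Study populations will be analyzed according to intention-to-treat principles".
- Item 28, loss to follow-up: "When data are missing due to loss to follow-up, baseline values will be imputed".
- Item 28, one sample missing: the rule begins "If only one time point 3 or 5 is missing (LDL cholesterol at d18 or d180), the mean LDL" and goes on to set that mean equal to the day 21 or day 183 value.

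Neither item 26a nor item 28 gives a separate denominator for the misclassification outcome or excludes imputed values from it. Item 28 also does not say whether day 0 or the day -3/0 mean stands in for a missing sample 4 or 6.

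**The concern.** The outcome asks how often two measurement rules disagree within the same person. Someone without follow-up samples carries no information on that. Under the plan as written, such a person still enters the denominator, with follow-up values built from baseline that make the two rules agree almost automatically. Someone missing only day 18 or 180 is given the same follow-up value under both rules, so the follow-up disagreement that the analysis is meant to measure is absent.

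Both rules push the reported proportion toward the conclusion that one sample is enough. Whatever the merits of baseline imputation as a cautious choice for the treatment comparison, they do not carry over to a question of measurement agreement.

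**Working it through.** **Inputs from the documents.** Within-person CV 7% for one sample and 5% for the mean of two (protocol, Statistical analyses); expected effect about 5% and planned loss of 20% in the intervention group (protocol, Statistical analyses; SAP item 11); 113 participants included (SAP item 11).

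**Assumptions, because the documents give no figure.** SD of the true percentage change between people: 0, 5 or 10 points. Pooled loss: 10% or 20%. With equal arms, 20% loss in one arm and none in the other gives (20% + 0%)/2 = 10%; 20% in both gives 20%. Share missing only day 18 or 180: 10%, for illustration.

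**The plan's own figure.** 7%/√2 = 4.95%, which rounds to the stated 5%. The documents state no expected misclassification rate.

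**Lost participants.** The double rule gives baseline mean/baseline mean - 1 = 0%, a non-responder. For the single rule there are two readings:

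- Day 0 carried forward: d0/d0 - 1 = 0%. Misclassification is exactly 0.
- Baseline mean carried forward: change = (d-3 + d0)/(2·d0) - 1. This is -10% or lower only if d-3 ≤ 0.8·d0. With independent 7% errors, the SD of e(-3) - 0.8·e(0) is 0.07 × √(1 + 0.64) = 0.0896, so the probability is Φ(-0.20/0.0896) = Φ(-2.23), about 1.3%.

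**Fully observed participants.** I used a simulation of 1,000,000 participants per scenario, each with four LDL values with independent 7% errors. Double rule: mean(d18, d21)/mean(d-3, d0). Single rule: d21/d0. Misclassified means that the two rules disagree on a reduction of at least 10%. Call this rate f.

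**Only day 18 or 180 missing.** Both rules use the same follow-up value and differ only in baseline. Call this rate g.

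Results at a mean change of -5% (computed from unrounded rates):

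| SD of true change (points) | 0 | 5 | 10 |
|---|---|---|---|
| f, all samples measured | 20.7% | 18.8% | 14.8% |
| g, only d18/d180 missing | 13.7% | 12.7% | 10.2% |
| 10% lost, d0 carried: 0.9f | 18.6% | 16.9% | 13.3% |
| 20% lost, d0 carried: 0.8f | 16.6% | 15.0% | 11.8% |
| 20% lost, mean carried: 0.8f + 0.2 × 1.3% | 16.8% | 15.3% | 12.1% |
| 20% lost, d0 carried, and 10% missing d18/d180: 0.7f + 0.1g | 15.9% | 14.4% | 11.3% |

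The ratio g/f at SD 5 is 12.7/18.8 = 0.68, a fall of about a third.

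**Other mean changes.** Over nine scenarios (mean change 0, -5% and -10%, each with the three SDs), f runs from 12.1% to 25.0% and g from 8.3% to 16.7%. The bias was downward in all nine.

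**Number against proportion.** With 113 participants and 20% lost, 113 × 0.8 = 90.4 have complete pairs. At 18.8%, 90.4 × 0.188 = 17.0 are misclassified. The proportion is 17.0/90.4 = 18.8% among complete pairs but 17.0/113 = 15.0% under the plan. Loss dilutes the proportion and leaves the number almost unchanged; substitution for day 18 or 180 lowers both.

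**The case against.** Several stronger readings are tempting and do not hold.

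- A reader might infer that imputed participants can never be misclassified. That requires day 0 to be the value carried forward for the single-sample rule. Item 28 does not say so, and the only LDL baseline that item 26c defines is the two-sample mean. On that reading about 1.3% of imputed participants are misclassified. The bias is barely smaller.
- A reader might infer that a missing day 18 or 180 removes all disagreement. It removes the follow-up part only; day 0 against the mean of days -3 and 0 can still put the person on different sides of the threshold.
- A reader might apply 20% loss to the whole trial at both time points. The documents give it for the intervention arm only, with nothing specific to 3 weeks.

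The direction also depends on the classes counted. Item 26a does not name them where it defines misclassification, and the same item lists three LDL response categories. With three categories and the baseline mean carried forward, about half of imputed participants change category and the bias reverses: 36.6% becomes 39.3% at a mean change of -5%, SD 5 points and 20% loss. The aim's responder/non-responder wording favours two classes, so this is the weaker reading. That an unstated imputation detail can turn the sign is a further reason to keep imputed values out.

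Finally, this is a descriptive secondary outcome. Item 16 calls such outcomes mainly hypothesis generating, and the documents set no rate above which double sampling would be judged necessary. Losses will be reported by group and timing (items 23 and 24), so a reader could roughly rescale. This limits the importance of the point, but the proportion reported under the plan would still be wrong for the question asked.

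**Conclusion.** The concern holds for the responder/non-responder outcome. As written, items 20 and 28 add near-automatic agreements to the denominator and remove follow-up disagreement where day 18 or 180 is missing. The proportion misclassified is biased downward, roughly in proportion to the loss: at a mean change of -5%, from 15-21% to about 12-17% at 20% pooled loss, or 13-19% at 10%.

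These sizes rest on the protocol's 7% CV, independent errors between samples and the assumed SD of true change of 0 to 10 points. Actual loss is not in the documents and may be lower, especially at 3 weeks. The number misclassified is little affected by loss. The point deserves correction because the outcome answers its own stated aim, but it does not touch the primary LDL comparison.

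**What to change.** Add to SAP items 26a and 28: the misclassification analysis classifies participants as responders or non-responders (at least 10% LDL reduction), uses only those with both LDL samples measured at baseline and both at the relevant follow-up, and admits no imputed or substituted LDL value. Report the number of complete pairs at 3 weeks and at 6 months as the denominator.

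As a safeguard, apply the same restriction to the day 18/21 and day 180/183 CV in item 26a. The effect on that outcome was not quantified here.

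The cost is one sentence and a smaller denominator for this secondary outcome. No new data are needed, and the primary intention-to-treat analysis stays as it is.

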### **Statistical analyses**

Based on previous randomized intervention studies of dietary fat quality and effects on lipoproteins, at least n=222 participants are required (for alpha = 0.05 and beta = 0.10) to detect an effect in LDL cholesterol of 0.175 mmol/L (~5%), which is an effect slightly exceeding that in most previous studies, parallels within-individual day-to-day variation (at double sampling), and has some clinical significance. This calculation takes into account a 20% loss to follow-up in the intervention group and a contamination effect of 5% in the control group.

The results will be analyzed according to intention-to-treat principle. Missing data at follow-up will be handled by imputing the baseline value. For LDL cholesterol, the mean value of the double analyses at days -3/0, 18/21 and 180/183 will be used. The CV of the biological variation will thus be decreased from 7 to 5%. Between-group comparisons for effects on all outcomes will be performed as a generalized linear model (GLM) in SPSS software, adjusted for factors *a priori* considered likely to modify effects (baseline values, BMI, age and sex). As sensitivity analyses, also unadjusted, non-parametric testing (Mann-Whitney U-test) will be performed. P<0.05 will be considered as statistically significant.

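### SAP item 28 has no single-sample rule when day 21 or day 183 is the missing LDL value, so a measured day-180 outcome would most naturally be replaced by baseline

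*SAP*

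**What the plan says.** SAP item 26c defines LDL at each follow-up as a two-sample mean: "values at 3 weeks will be calculated as the arithmetic mean of values at days 18 and 21 [(d18+d21)/2"], and likewise "values at 6 months will be calculated as the arithmetic mean of values at days 180 and 183". Neither mean can be formed from one sample without a further rule.

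SAP item 28 has two rules. The general one is "When data are missing due to loss to follow-up, baseline values will be imputed". The exception begins "If only one time point 3 or 5 is missing (LDL cholesterol at d18 or d180") and continues that the mean "cholesterol value will instead be assumed to be the exact value at time point 4 or 6 (d21 or d183"). No sentence deals with the reverse case, where the earlier sample exists and the later one does not.

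The protocol (Statistical analyses) is broader: "Missing data at follow-up will be handled by imputing the baseline value". It is not limited to loss to follow-up and has no single-sample exception.

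Two other places bear on the reading. SAP item 19a ties completion to the last visit: "Being randomized and completing the trial (day 183) is considered as sufficient for adherence". The protocol (Methods) makes days 18 and 180 LDL-only visits, so a day-180 sample is a real measurement of the primary outcome. SAP item 26a names change in LDL at 6 months as the primary analysis.

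**The concern.** The plan accepts a lone day-183 value as the 6-month LDL but does not say the same of a lone day-180 value. If baseline is used instead, a change that was measured is recorded as zero in the primary analysis, and the participant moves to the lowest category of the LDL success outcome. At 3 weeks the same question decides who is a responder, and item 26a reports LDL change in that group separately. This is distinct from how participants with no follow-up sample are imputed, because here the outcome was observed. Under item 10 allocation is concealed only until data collection is complete, so a rule left open could be settled with allocation known.

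**Working it through.** **The plan's own figures.** The protocol says that double sampling lowers the biological CV from 7% to 5%. This reproduces: 7/√2 = 4.95%. The sample size of 222 cannot be reproduced because no SD is given, but the point does not depend on it.

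**Which rule applies to each incomplete pair.**

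| Missing | Measured | SAP item 28 | Protocol |
|---|---|---|---|
| d18 or d180 | d21 or d183 | Use the measured sample | Baseline |
| d183, participant then lost | d180 | Most naturally baseline (loss to follow-up) | Baseline |
| d21, participant returns at 6 months | d18 | No rule; not lost to follow-up | Baseline |
| Both samples, participant lost | None | Baseline | Baseline |

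Baseline in the second row is an inference from three things: the protocol rule has no exception, completion is day 183, and item 28 words its one-sample rule as a departure from baseline imputation.

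**One participant.** The effect of 0.175 mmol/L is given as about 5%, which implies a baseline near 0.175/0.05 = 3.5 mmol/L. Suppose day 180 is 3.0 mmol/L and day 183 is missing.
- Measured value used: (3.0 − 3.5)/3.5 = −14.3%, in the category of a 10% or greater reduction.
- Baseline used: 0%, in the category of no reduction.

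**Effect on the between-group difference.** Let f be the share of each arm with day 180 only. The documents do not give f, so the range is assumed. If f is equal in both arms and these participants respond like the rest, the expected difference is 0.175 × (1 − f).
- f = 2%: loss 0.175 × 0.02 = 0.0035, about 0.004 mmol/L.
- f = 6%: loss 0.175 × 0.06 = 0.0105, about 0.011 mmol/L.

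With 113 participants this is 2.3 to 6.8 people in total.

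**Power.** The SD has to be solved backwards from N = 222 (two-sided alpha 0.05 assumed, power 0.90): SD = δ√(n/2)/(1.960 + 1.282), with n = 111 per arm. With δ = 0.175 this gives 0.402. With δ reduced by 25% (20% loss plus 5% contamination, treated as dilution) it gives 0.302. Holding the SD fixed, with N = 113:

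| f | Expected difference | Power, SD 0.302 | Power, SD 0.402 |
|---|---|---|---|
| 0 (measured value used) | 0.175 | 87% | 64% |
| 2% | 0.1715 | 86% | 62% |
| 5% | 0.166 | 83% | 59% |
| 10% | 0.1575 | 79% | 55% |

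**Unequal shares.** Write c for the mean change in controls and c − 0.175 for the intervention arm, with affected shares f_I and f_C. The expected difference becomes −0.175(1 − f_I) + c(f_C − f_I). With f_I = 2% and f_C = 6%, it exceeds 0.175 in size when controls fall by more than 0.0035/0.04 = 0.0875 mmol/L. The direction is therefore not fixed.

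**The case against.** The strongest reply is that item 28 never says a participant sampled on day 180 is lost to follow-up. Item 19a defines adherence, not missing data, and the SAP is narrower than the protocol. That stands: baseline imputation here is the natural reading, not a stated instruction.

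Second, few people should be affected. Item 19a allows two weeks' deviation around day 183, so a late sample can still complete the pair. The 500 SEK is paid only after the final samples, which gives someone who came on day 180 a reason to return. This also stands and is why the size is put as probably small.

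Third, the two samples differ in role. Days 21 and 183 are the full fasting visits, fasting deviations are recorded only at time points 2, 4 and 6, and the misclassification analysis keeps only those samples. Treating the later sample as the reference fits that structure. But the SAP does not offer it as a reason, and days 18 and 180 exist to measure LDL. It does not justify replacing a measured value with baseline.

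A reader might also infer that the observed change could be halved, by putting baseline in the day-183 slot and averaging it with day 180. The documents describe no such calculation.

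**Conclusion.** The asymmetry is real and should be corrected. For a participant with day 180 who is lost before day 183, the SAP and protocol together most naturally replace a measured primary outcome with baseline and turn an observed responder into a non-responder.

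Two stronger readings are not supported. One is that the SAP itself imposes baseline whenever the second sample of a pair is missing: for a missed day 21 in someone who returns at 6 months, the loss-to-follow-up condition is not met and only the protocol sentence leads there. The other is that the bias is always towards zero: that needs assumptions such as similar affected shares and similar responses in the two arms.

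Under those assumptions, 2–6% affected costs about 0.004–0.011 of 0.175 mmol/L. At 5% the power loss is 4 to 5 points. Both figures rest on an assumed f, and the power figures also on a back-solved SD. The case for acting is that measured primary outcomes should not be discarded and that the remedy is very cheap.

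**What to change.** Amend item 28 to say three things. If exactly one sample of a follow-up pair (d18/d21 or d180/d183) is available, that value is the LDL value for the time point. Baseline imputation applies only when both samples of the pair are missing. The number of single-sample values is reported per arm and time point. The protocol's missing-data sentence should be read subject to this rule. It should be settled before allocation is revealed or, failing that, dated and labelled as a later decision.

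The cost is one short SAP change and a count in the results. The single values are noisier, with a biological CV of about 7% instead of 5%, which the SAP already accepts when day 18 or day 180 is the missing sample.
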